2.0 Outcomes

2.1 Primary outcome: The primary efficacy endpoint of this double-blind, placebo-controlled phase IIa trial is a binary indicator for whether a patient would be alive and free of invasive mechanical ventilation at 28 days. The outcome will be summarized as the proportion of patients alive and free of invasive mechanical ventilation at 28 days in those receiving dupilumab in addition to standard of care (treatment arm) compared to those receiving solely standard of care management (placebo arm).

2.2 Secondary outcomes:

2.2.1 Eosinophilia as the safety outcome: The safety endpoint of this study is a binary indicator for whether a patient would have eosinophilia, which is defined as an absolute eosinophil count $> 0.6 \text{ k}/\mu\text{l}$ at ≥ 1 measurement throughout the study period. The outcome will be summarized as the proportion of patients with eosinophilia for treatment arm and placebo arm respectively. Complete blood counts with differentials

and complete metabolic panels will be measured on Day 0, 2, 5, 7, 14, 28 and 60. Day 7, 28 and 60 optional, although recommended, if patient discharged within the time frame.

2.2.2 **Other secondary safety and efficacy outcomes:**

- Cumulative incidence (defined as number of new events divided by the total number of individuals in the population at risk for the time interval) of grade 3 and 4 adverse events, serious adverse events or death including: injection site reactions, eye/eyelid inflammation, conjunctivitis, oropharyngeal pain, insomnia, tooth ache, gastritis, arthralgia, bacterial pneumonia, herpes viral infection, hypereosinophilic syndrome, hypersensitivity reaction.
- Prevalence of B.1.1.7 and B.1.351 and other SARS-CoV-2 lineages in study cohort: Day 0.
- Plasma total Immunoglobulin E (IgE) levels: Day 0 and 14.
- Plasma inflammatory markers (C-reactive protein and ferritin): Day 0, 7 and 14. Day 7 optional if patient discharged.
- Plasma cytokine levels including TARC (CCL17), YKL40, eotaxin 3 (CCL26), IL-13, IL-4, Arg1, Hyaluronan, soluble ST2: Day 0, 2, 5, 7, 14, and 28. Day 7 and 28 optional if patient discharged.
- Change in PaO₂/SaO₂ to FiO₂ ratio: Day 0, 2, 5, 7 (if patient remains inpatient throughout)
- All-cause mortality rate at 28 days.
- Hospital length of stay (LOS)
- ICU LOS
- Proportion of patients alive and free of invasive respiratory failure at 28 days.
- Proportion of patients alive and free of invasive mechanical ventilation at 60 days.

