3.0 General considerations

3.1 Analysis populations: Each primary and secondary efficacy outcome measure will be analyzed for the intent-to-treat (ITT) and evaluable population. The intent-to-treat principle is that participants will be analyzed in the groups to which they were randomized, regardless of whether they received the randomized study medication. Another analysis population of interest is the as-treated population. The as-treated population will consist of only participants who were inducted onto study medication, even one dose of drug. Safety outcome will be primarily analyzed for the as-treated population.

Major differences in the results for the ITT and as-treated populations, if any, will be further explored. While there is every intention to be complete in describing the analyses to be performed, it is not possible to anticipate every contingency, and some adjustments may be required to meet constraints posed by the structure of the data. Constraints such as non-linearity, non-normality, etc. may lead to different but more appropriate approaches to analysis.

3.2 Testing of Distribution assumptions: Empirical distributions of all variables will be visually inspected to detect outliers. The underlying proposed statistical methods for each analysis will be examined, primarily through inspection of graphical displays, standardized residuals, or influence diagnostics. Where appropriate and/or necessary, transformations will be utilized for continuous measures such as biomarker data, or categorized biomarkers will be analyzed.

3.3 Interim analysis: there is no formal scheduled interim analysis with respect to the primary efficacy outcome and thus the sample size estimation would not be altered. However, analysis for some selected biomarkers will be performed after the 14th day of the 20th patient enrolled. Particularly, the proportion and rate of change of C- reactive protein and ferritin levels will be calculated from day 0 and day 14 time points to determine efficacy trends between the two treatment groups. Additionally, percentage of eosinophilia will be calculated between the two groups to determine safety trend. Data will be analyzed by a third party and remain blinded to the study investigators. We expect greater changes in C-reactive protein and ferritin for patients receiving Dupilumab than those receiving placebo and no significant differences in eosinophilia between the two groups.

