- Plasma inflammatory markers (C-reactive protein and ferritin) on Day 0, 7 and 14 (Day 7 would be optional if patient discharged) will be analyzed as longitudinal responses in the linear mixed effects model with Dupilumab treatment as a fixed effect. Since this is a randomized study, significant effect of treatment on intercept is not expected. Thus, the longitudinal analysis will focus on the slope difference between the treatment arms via interaction of treatment and time in the model. Since there are only 3 measures for each subject, only random slopes will be specified as *a priori*. Model fitting indices will be examined carefully to ensure the validity of estimated parameters. If Day 7 data won't be available for all patients, these biomarkers between Day 0 to Day 14 will be analyzed as the IgE above.
- Plasma cytokine levels including TARC (CCL17), YKL40, eotaxin 3 (CCL26), IL-13, IL-4, Arg 1, Hyaluronan, soluble ST2 on Day 0, 2, 5, 7, 14, and 28 (Day 7 and 28 optional if patient discharged) will be analyzed as longitudinal responses

in the linear mixed effects model with Dupilumab treatment as a fixed effect, and with appropriate transformation of biomarkers if necessary. The trajectories of these biomarkers will be carefully evaluated, and the slope difference between the treatment arms will be evaluated by the interaction of treatment and time.

Additional curvature in trajectories will also be explored and captured whenever possible in the linear mixed effects model.

- Change in $\text{PaO}_2/\text{SaO}_2$ to FiO_2 ratio on Day 0, 2, 5, 7 (if patient remains inpatient throughout) will be analyzed as longitudinal responses in the linear mixed effects model, similar methods to that for inflammatory biomarkers and cytokine biomarkers as described above.
- All-cause mortality at 28 days will be analyzed as the binary response, using the same methods as that for the primary efficacy outcome and eosinophilia.
- Hospital length of stay (LOS) and ICU LOS between treatment arms will be analyzed as continuous measures using t-test or Wilcoxon test initially, and adjusted difference and its 95% CI will be estimated from linear regression. Since the distributions of hospital LOS and ICU LOS are often skewed, the log-transformed LOS data will be considered in the analyses.
- The response of being alive and free respiratory failure at 28 days is a binary response and will be analyzed using the same methods as that for the primary efficacy outcome.

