8.0 Missing data

Since patients in this study will be closely followed for mortality and status on mechanical ventilation, the primary outcome of being alive and free of ventilation is likely captured. Dropout from the study will be carefully evaluated for its potential informativeness. A sensitivity analysis will be performed to examine the impact on the proportion and its confidence limits. In particular for the primary endpoint, individuals who withdraw will be considered events if their statuses on day 28 are unknown.

Other outcome variables (clinical conditions and laboratory biomarkers) will have missing data due to dropout from treatment and/or from study participation, or due to missed outpatient visits if patients have been discharged from the hospital. The generalized linear model, or mixed effects model frameworks that will be used for analyses, works with what data are gathered, and assumes missing data are missing at random. For selected secondary outcome analyses, sensitivity analyses will be considered to examine the stability of estimated treatment effects in the face of departures from the assumption of missing at random.

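### Read literally, the random-slopes-only model for CRP and ferritin gives a wrong standard error for the slope difference, in a direction the documents cannot fix

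*SAP*

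**What the plan says.** SAP 2.2.2 lists "Plasma inflammatory markers (C-reactive protein and ferritin): Day 0, 7 and 14", with Day 7 optional once a patient is discharged. SAP 5.3.2 analyses the three visits in a linear mixed model with treatment as a fixed effect, and "the longitudinal analysis will focus on the slope difference between the treatment arms via interaction of treatment and time in the model".

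On the random part it says: "Since there are only 3 measures for each subject, only random slopes will be specified as" the a priori choice. The only other reason offered is that, under randomization, no treatment effect on the intercept is expected. The section gives no random intercept, time coding, residual covariance structure or robust standard error.

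Three provisions might soften this:
- SAP 5.3.2: "Model fitting indices will be examined carefully to ensure the validity of estimated parameters".
- SAP 5.3.2: "If Day 7 data won't be available for all patients, these biomarkers between Day 0 to Day 14 will be analyzed as the IgE above".
- SAP 3.1: constraints in the data "may lead to different but more appropriate approaches to analysis".

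SAP 3.4 tests at 5% two-sided and promises confidence intervals where possible. On the expected result, SAP 3.3 says: "We expect greater changes in C-reactive protein and ferritin for patients receiving Dupilumab than those receiving placebo".

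**The concern.** Patients differ in CRP and ferritin on Day 0, and a patient who starts high may stay relatively high. A random slope multiplied by a time of zero contributes nothing at Day 0, so the literal model has no term that links a patient's Day 0 value to later ones.

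Neither stated reason supports leaving that term out. The expectation about the intercept concerns arm means, and randomization does not remove between-patient spread at Day 0. Three visits supply three variances and three covariances, six quantities in all; a correlated random intercept and slope plus residual variance needs four.

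At stake is the width of the interval and the validity of the test for the quantity that SAP 5.3.2 makes the focus for these markers. An interval that is too wide can hide a real change, and one that is too narrow can suggest a change that is not there.

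**Working it through.** The SAP gives no variance, standard error or power for this model, so there is no figure of its own to reproduce. Inputs from the documents are 40 patients randomized 1:1, hence 20 per arm (SAP 1.2), visits at Days 0, 7 and 14, and a 5% two-sided test (SAP 3.4). **All SDs and correlations below are assumptions.**

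**1. Implied covariance.** Take Y = fixed part + b·t + e with t = 0, 1, 2 weeks, Var(b) = τ², Var(e) = σ² and independent residuals. Then:
- Cov(Day 0, Day 7) = Cov(Day 0, Day 14) = 0.
- The variances are σ², σ² + τ² and σ² + 4τ², so they cannot fall.

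**2. Estimate and standard error.** With complete, equally spaced data the fitted slope difference equals the between-arm difference in mean Day 0 to Day 14 change (divided by 2 if expressed per week). It does not depend on the covariance model. On the change scale:
- True SE² = (2/20)·Var(Y14 − Y0).
- Model SE² = (2/20)·(2σ² + 4τ²).

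**3. Stable variance, persistent levels.** SDs 1/1/1, all correlations 0.5.
- True: Var(change) = 1 + 1 − 2(0.5) = 1.00, so SE = √0.100 = 0.316.
- Model: REML tends to σ² = 0.792 and τ² = 0.122, giving 2(0.792) + 4(0.122) = 2.07, so SE = √0.207 = 0.455.
- Ratio: √2.07 = 1.44. Type I error ≈ 2[1 − Φ(1.96 × 1.44)] ≈ 0.5%.
- Simulated power for a difference of 0.6 Day 0 SD is 16%, against 46% for a t-test of change.

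**4. Falling variance, weak link to Day 14.** SDs 1/0.4/0.3, adjacent-visit correlation 0.2, Day 0–14 correlation 0.2² = 0.04.
- True: 1 + 0.09 − 2(0.04)(0.3) = 1.066, so SE = √0.1066 = 0.326.
- Model: it cannot represent a falling variance, so τ² goes to 0. Var(Y0 − 2Y7 + Y14)/6 = 1.338/6 = 0.223, and σ² = [38(1 + 0.16 + 0.09) + 2(0.223)]/116 = 0.413. Then 2σ² = 0.827, so SE = √0.0827 = 0.288.
- Ratio: √(0.827/1.066) = 0.88. Simulated type I error is 7.9%.

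**5. What decides the direction.** Suppose the truth has random-intercept variance vi, slope variance vs per week², intercept–slope covariance c and residual variance 1. Per week, true SE² = 0.1(0.5 + vs). While τ² is estimated above zero, the model reports about 0.1(0.5 + vs + 0.535vi + 1.2c). It is therefore too large unless c is below −(0.535/1.2)vi ≈ −0.45vi.
- Step 3 is vi = 1, vs = 0, c = 0 in these units: √(1.035/0.5) = 1.44.
- With vi = vs = 1 and correlation −0.8, c = −0.8: √(1.075/1.5) = 0.85, type I error 9.7%.

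**6. Range.** Model SE divided by true SE, 20 per arm, complete data, simulated (figures good to about 0.01). Decaying means r between adjacent visits and r² between Days 0 and 14.

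| SDs, Day 0/7/14 | Equal correlation 0.2 / 0.5 / 0.7 | Decaying, r = 0.2 / 0.5 / 0.7 |
|---|---|---|
| 1/1/1 | 1.13 / 1.44 / 1.87 | 1.03 / 1.17 / 1.44 |
| 1/0.7/0.5 | 1.05 / 1.24 / 1.44 | 0.98 / 1.08 / 1.24 |
| 1/0.5/0.4 | 0.97 / 1.11 / 1.25 | 0.91 / 0.98 / 1.10 |
| 1/0.4/0.3 | 0.92 / 1.02 / 1.11 | 0.88 / 0.93 / 1.01 |

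Across this table the type I error runs from under 0.1% to about 8%. A t-test of Day 0 to Day 14 change held 4.9% to 5.1% in the equal-correlation settings.

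**The case against.** The strongest objection is that the sentence may have meant something else: linear random terms only and no random curvature, with an intercept taken for granted. The next item in SAP 5.3.2, on cytokines at six visits, does speak of exploring curvature, and on that reading the three-measure reason makes sense. This stands as a reason to ask for clarification. It does not remove the point, because the literal text says only slopes.

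The two premises in step 1 are also not in the SAP. An unstructured residual covariance would remove the problem, and another time origin would change it. So the result is conditional.

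The model may also seldom be run. Day 7 is optional after discharge, and if one missing Day 7 value triggers the Day 0/Day 14 fallback, the fault never appears. But the trigger can be read as not for every patient or as not for any patient. The t-test or Wilcoxon planned first for biomarkers in SAP 5.1 is likewise free of the fault. The fit-index sentence and the flexibility clause permit a repair, but neither names an alternative model or a rule for adopting one.

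A reader might infer that the planned test is simply conservative. The documents do not support this: they give no variances or correlations, and step 6 shows errors in both directions. A marker that falls most in the patients who start highest pushes the ratio down.

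A reader might also infer that the slope difference itself is biased. With complete data it is not. SAP 8.0 does expect "missing data due to dropout from treatment and/or from study participation, or due to missed outpatient visits if patients have been discharged". In one constructed case, with Day 14 missing in about 6 of 20 patients in one arm, more often after a low Day 7 value, the bias was at most 0.06 Day 0 SD. That is too small, and too dependent on the assumed mechanism, to carry the point.

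**Conclusion.** The point holds in conditional form and is minor. If the model is fitted as written, with Day 0 as time zero and independent residuals, the standard error of the CRP and ferritin slope difference is generally wrong. Under the assumed settings with 20 per arm, it ranges from about 0.85 to about 1.87 of its true value. It is too large when levels persist and variance is stable. It is too small when variance falls steeply and the Day 0–14 correlation is low. The documents cannot say which applies.

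The consequence is limited to interval width and test validity for two secondary markers of the parent trial, which SAP 5.1 and 7.0 describe as proof of concept. The Day 0/Day 14 fallback and the initial two-sample tests are unaffected. Nothing here touches the parent trial's primary outcome, and the extension protocol does not name CRP or ferritin among its endpoints.

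**What to change.** In SAP 5.3.2, replace the random-slopes-only specification for CRP and ferritin with an unstructured covariance over the three visits, or with a correlated random intercept and slope, and add a small-sample correction such as Kenward-Roger. If an intercept was always intended, say so, and state the time coding and residual structure. State also whether the Day 0/Day 14 fallback applies when any patient lacks Day 7 or only when Day 7 is absent throughout. Because the Protocol summary reports that parent-trial enrollment closed in November 2021 and describes its findings, report the result as a labelled corrected or sensitivity analysis.

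The cost is about a sentence of text and a line of SAS for the model, plus a sentence on the trigger. There are three downsides:
- A few more covariance parameters must be estimated.
- Without the small-sample correction the unstructured standard error is slightly small at 20 per arm (ratio 0.94 to 0.99, type I error 4.5% to 7.0%). The intercept-plus-slope model gave 1.02 to 1.07 and 3.2% to 5.2%. Both come from 1,000 trials per setting, with a Monte Carlo error of about 0.7 points. Kenward-Roger itself was not simulated.
- If the time course is not linear, the unstructured model's weighted slope need not equal the Day 0 to Day 14 change, so that change should be reported beside it.

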5.3 Secondary outcomes

5.3.1 Eosinophilia as the safety outcome: Eosinophilia is a binary indicator for a patient

to have an absolute eosinophil count $> 0.6 \text{ k}/\mu\text{l}$ at ≥ 1 measurement based on the blood counts with differentials and complete metabolic panels on Day 0, 2, 5, 7, 14, 28 and 60 (Data on Day 7, 28 and 60 would be optional). The outcome will be summarized as the proportion of patients with eosinophilia and the difference in the proportions between the two study arms will be evaluated with Chi-square test. The odds ratio of having eosinophilia for Dupilumab vs. placebo and its 95% CI will also be estimated in logistic regression, with adjustment for other covariates.

5.3.2 Other secondary safety and efficacy outcomes:

- Cumulative incidence rate of adverse events (injection site reactions, eye/eyelid inflammation, conjunctivitis, oropharyngeal pain, insomnia, tooth ache, gastritis, arthralgia, bacterial pneumonia, herpes viral infection, hypereosinophilic syndrome, hypersensitivity reaction, other grade 3 or 4 adverse events, serious adverse events or death) is defined as number of adverse events divided by the total number of individuals in the population at risk for the time interval. The rate ratio of adverse events for Dupilumab vs. placebo and its 95% CI will be analyzed in Poisson regression, in which the follow-up time interval will be considered as the offset. Adjusted analysis for other covariates will be performed, as necessary. Mortality at 60 days will be analyzed as the time to event response. Survival probabilities will be estimated by the Kaplan-Meier method, and the difference in the mortality risk between the two treatment groups will be evaluated by the log-rank test and further in Cox regression, adjusting for the baseline covariates. For the analysis of mortality over the first year, additional adjustment for dynamic mechanical ventilation effect will be considered by including being on ventilation as a time-vary covariate in the Cox regression.
- Plasma total Immunoglobulin E (IgE) levels on Day 0 and 14 will be considered as continuous responses, and difference between treatment arms will be evaluated by t-test or Wilcoxon test initially, and adjusted difference and its 95% CI will be estimated from linear regression. Further, changes of IgE from Day 0 to Day 14 will also be explored and the difference between the two study arms will be analyzed similarly.

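### For C-reactive protein and ferritin, incomplete Day 7 data would replace the mixed model with a two-visit analysis; this is likely to happen, conflicts with the rest of the SAP and costs little precision

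*SAP*

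**What the plan says.** SAP 2.2.2 lists C-reactive protein and ferritin at "Day 0, 7 and 14. Day 7 optional if patient discharged". SAP 5.3.2 says that these markers "will be analyzed as longitudinal responses in the linear mixed effects model with Dupilumab treatment as a fixed effect", with interest in the treatment-by-time slope and with random slopes but no random intercept.

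The same bullet then sets a condition, "If Day 7 data won't be available for all patients", under which "these biomarkers between Day 0 to Day 14 will be analyzed as the IgE above". No proportion or threshold is attached to it.

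For IgE, SAP 5.3.2 says that the "difference between treatment arms will be evaluated by t-test or Wilcoxon test initially". An adjusted difference then comes from linear regression, and "changes of IgE from Day 0 to Day 14 will also be explored".

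Two other places bear on this:

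- The next bullet of SAP 5.3.2 keeps a mixed model for the cytokines, whose Day 7 and Day 28 samples are also optional after discharge. It has no fallback.
- SAP 8.0 expects missing values from missed visits after discharge, and says that the generalized linear or mixed model framework "works with what data are gathered, and assumes missing data are missing at random".

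**The concern.** A mixed model does not need every patient to have every visit. Here, incomplete data at one optional visit is the reason for giving the model up. A patient with Days 0 and 7 but no Day 14, for example one who dies or leaves in between, would contribute to the mixed model but adds no post-baseline information to the two-visit analysis. The pattern of missing data would also choose the analysis, without a stated reason for treating these two markers differently from the cytokines. They are also the two markers that SAP 3.3 selects for the mid-trial look at efficacy trends.

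**Working it through.** The plan gives no figure to reproduce. The checks are how likely the switch is, what it costs, and whether the replacement model has problems of its own.

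**1. Chance of the switch.** Input: 40 patients (SAP 1.2; Protocol 6.2 confirms that 40 were enrolled). The risk *p* that a patient lacks Day 7 is not in the documents, so it is varied. Assuming independence, the chance that at least one patient lacks Day 7 is 1 − (1 − *p*)^40.

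| *p* (assumed) | Chance of switch |
|---|---|
| 1% | 33% |
| 2% | 55% |
| 5% | 87% |
| 10% | 98.5% |

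It reaches 95% at *p* = 1 − 0.05^(1/40) = 7.2%, or about 3 of 40 patients.

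**2. What Day 7 adds to a linear slope.** For days 0, 7 and 14 the sum of squares about the mean day is 49 + 0 + 49 = 98. The slope weights are −7/98, 0 and +7/98, that is −1/14, 0 and +1/14. Day 7 adds nothing to the linear slope for a patient who has Days 0 and 14. Any loss comes from patients without Day 14, and from curvature that two visits cannot show.

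**3. Precision lost.** The table gives the variance of the two-visit change analysis divided by that of the linear-slope mixed model. Values are missing at random and 0 to 50% of Day 7 values are absent. Three covariances were assumed: random slope only; random intercept and slope; equal correlation of 0.5.

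| Day 14 missing (assumed) | Variance ratio |
|---|---|
| 0% | 1.00 |
| 10% | 1.03 to 1.05 |
| 20% | 1.06 to 1.10 |
| 30% | 1.10 to 1.17 |

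The documents give no Day 14 missing rate. The nearest figure is 7 deaths among 40 patients by Day 60 (Protocol 6.2), with no timing.

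**4. The same comparison with visit as a category.** Take unit variances, equal correlation of 0.5, Day 7 complete and a fraction *m* missing Day 14. Given Days 0 and 7, Day 14 has residual variance 2/3. The variance of the remaining part of the change is 1/3. Per patient:

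- Mixed model: 1/3 + (2/3)/(1 − *m*).
- Two-visit change: 1/(1 − *m*).
- At *m* = 10%: 1.111/1.074 = 1.03. At *m* = 20%: 1.250/1.167 = 1.07.

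**5. Curved decline under a linear slope.** Assume log means of 4.5, 2.5 and 2.0 in both arms, so no treatment effect. A complete patient has slope −2.5/14 with weight 98, contributing −17.5. A patient with Days 0 and 7 only has slope −2/7 with weight 24.5, contributing −7. Suppose that 1 of 20 patients in one arm and 4 of 20 in the other lack Day 14. Using within-patient information:

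- Arm 1: (19 × −17.5 − 7)/(19 × 98 + 24.5) = −339.5/1886.5 = −0.1800 per day, or −2.52 over 14 days.
- Arm 2: (16 × −17.5 − 28)/(16 × 98 + 98) = −308/1666 = −0.1849 per day, or −2.59 over 14 days.
- Spurious difference: about 0.07.
- Standard error with within-patient variance 0.5: 14 × √(0.5/1886.5 + 0.5/1666) = 0.33. The difference is about a fifth of that.

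With visit as a category the three means are estimated freely, and this distortion disappears.

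**The case against.** The strongest defence is that the fallback keeps the contrast that matters. SAP 3.3 already uses Day 0 and Day 14 for these markers, only Day 7 is optional for them, and step 2 shows that Day 7 has no weight in the linear slope when Day 14 is present. That stands, and it is why the cost is small.

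The IgE method also includes linear regression. If that regression adjusts for baseline (the covariates are not listed), its variance relative to the raw change is (1 + ρ)/2, or 0.70 to 0.80 at an assumed correlation ρ of 0.4 to 0.6. This also stands, but a mixed model can adjust for baseline too. With ρ = 0.5, residual variance given baseline is 0.75, of which Day 7 explains one ninth (0.083). At 20% missing Day 14 the ratio is then (0.75/0.8)/(0.083 + 0.667/0.8) = 0.9375/0.9167 = 1.02. Against a baseline-adjusted regression the loss is therefore about 2%.

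A reader might infer more than the documents support:

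- **That the mixed model would never be run.** This needs a Day 7 missing rate that the documents do not give. At 1% the switch has a 33% chance. The condition could also mean that no patient has Day 7, which would make the switch remote. Because "Day 7 optional if patient discharged" applies patient by patient, the other reading is more natural, but the wording is unclear.
- **That section 8.0 is directly contradicted.** It does not say why the mixed model was chosen, and its framework includes generalized linear models, so the fallback regression falls within it. The inconsistency lies in dropping observed data because other data are missing.
- **That the fallback is wholly a complete-case analysis.** This is true of the change analysis. A Day 14 comparison needs only Day 14.
- **That results would be biased by the switch.** No calculation here shows that. Step 5 shows a small bias in the linear mixed model itself.
- **That deleting the sentence has no downside.** Deletion alone leaves the linear model without a random intercept in force.

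**Conclusion.** The point holds, at low severity. On the natural reading, a single missing Day 7 value replaces the planned model, and because Day 7 is optional after discharge this is likely: 87% at an assumed 5% missing and 98.5% at 10%, with 40 patients and independence. The rule is inconsistent with the cytokine bullet and sits badly with section 8.0.

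The cost is nil for the linear slope if Day 14 is complete. It is roughly 3 to 10% more variance for the change analysis at 10 to 20% missing Day 14, and less against a baseline-adjusted regression. These sizes rest on assumed missing rates and covariances. The markers are secondary outcomes in the exploratory parent trial, and no conclusion is shown to change.

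**What to change.** In SAP 5.3.2:

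- Delete the fallback sentence. Fit one mixed model to all available Day 0, 7 and 14 values, whether or not Day 7 is complete.
- Replace the random-slopes-only specification with a random intercept or an unstructured covariance.
- Treat visit as a category and take the Day 14 contrast between arms as the result, so that curved decline does not distort it.
- Report the baseline-adjusted regression of Day 14 as a sensitivity analysis.

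The cost is a few extra parameters and slightly more analysis work. The fixed effects rise from four (an intercept and slope per arm) to six (three visit means per arm). An unstructured covariance has six parameters instead of two. No new data are needed. Since Protocol 6.2 shows that enrolment in the parent trial is complete, if the fallback has already been used, the all-data model should be reported beside it.
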